Study Design	
This Phase 2a study will be conducted in approximately 40 study sites in the United States (US) and the European Union (EU). The study will comprise 2 sequential parts (subjects can only participate in either Part 1 or Part 2 of the study):
 
• Part 1: A Safety Run-in period to evaluate 2 predefined doses (7.5 mg/kg and 10 mg/kg) of imalumab given every week (QW) in combination with infusional 5-FU/LV given every 2 weeks (Q2W) in subjects with mutated tumors (KRAS mut, and/or NRAS mut), or imalumab in combination with panitumumab given Q2W in subjects with wild type tumors (KRAS wt and NRAS wt). Prior to entry into the study, subjects will be stratified according to their KRAS/NRAS mutation status. Treatments will be administered in 4-week (28-day) cycles.

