
1. Provision of a signed informed consent2. Male and female subjects 18 years of age and older at the time of screening3. Subjects who progressed after receiving at least 2, but no more than 3, prior cancer drug therapy treatment lines including SoC in the metastatic setting4. Anticipated life expectancy > 3 months at the time of screening5. Weight between 40 kg and 180 kg6. Histologically or cytologically confirmed diagnosis of CRC7. Metastatic CRC not amenable to surgical resection8. Known KRAS, NRAS mutation status (if unknown status for either of these genes, and no archival tissue is available, a fresh tumor biopsy will be obtained)9. At least 1 measurable lesion as defined by RECIST v1.110. Eastern Cooperative Oncology Group (ECOG) Performance Status (PS) of 0-211. Adequate hematological function, defined as:
a. Platelet count \geq 100,000/μLb. Prothrombin time and activated partial thromboplastin time (aPTT) $<$ 1.5 times the upper limit of normal (ULN)c. Absolute neutrophil count (ANC) \geq 1,000/μLd. Hemoglobin \geq 9 g/dL, without the need for transfusion in the 2 weeks prior to screening12. Adequate renal function, defined as serum creatinine \leq 2.0 times ULN and creatinine clearance $>$ 50 mL/min or estimated glomerular filtration rate $>$ 50ml/min/1.73 m²13. Adequate liver function, defined as:
a. Aspartate aminotransferase (AST) and alanine aminotransferase (ALT) \leq 2.5 times ULN for subjects without liver metastases, or \leq 5 times ULN in the presence of liver metastasesb. Bilirubin \leq 2.0 times ULN, unless subject has known Gilbert's syndrome14. Adequate venous access15. For female subjects of childbearing potential, the subject presents with a negative serum pregnancy test at screening and agrees to employ 2 forms of adequate birth control methods, including at least 1 barrier method (eg, diaphragm with spermicidal jelly or foam, or [for male partner] condom) throughout the course of the study and for at least 90 days after the last administration of imalumab. In addition, these birth control methods must be continued for at least 180 days after last administration of 5-FU in subjects who receive this treatment. Secondary contraceptive measures could be either birth control pills, patches, or intrauterine devices	

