6.1.5.4 Rationale for Selection of Combination Therapies

5-Fluorouracil and Leucovorin

The options for third- or fourth-line treatment are few, and 5-fluorouracil (5-FU)/leucovorin (LV) is part of standard of care (SoC). This regimen can be given regardless of Kirsten rat sarcoma viral oncogene homolog (KRAS) status and is well tolerated in this late-line setting when quality of life becomes an important parameter.

Panitumumab

Panitumumab is an approved option for third or fourth line monotherapy for subjects with KRAS wt tumors. Recently, using the novel technique of massively parallel multigene sequencing (also known as NGS), it has been shown that patients who benefit from panitumumab are those with all-RAS wt tumors, ie, those with no mutation in KRAS and neuroblastoma RAS viral (v-ras) oncogene homolog (NRAS) exons 2, 3, 4 at codons 12, 13, 61, 117, 141.^{29; 30; 31} The role of BRAF mutation as predictive of responsiveness to anti-EGFR monoclonal antibodies remains to be further validated. On the other hand, panitumumab is better tolerated than cetuximab because it is a fully humanized monoclonal antibody and it is better tolerated than another approved targeted agent, regorafenib, which yields severe toxicity in the majority of subjects. In this study, subjects will be tested for KRAS and NRAS mutation status, and only those with all-RAS wt tumor will be eligible for treatment with panitumumab.

Panitumumab has been approved in several countries including the United States (US) and Germany as standard therapy. The sponsor feels it is justified to administer panitumumab to subjects in this study with Eastern Cooperative Oncology Group (ECOG) Performance Status (PS) of 0-2. Panitumumab has been shown to be well tolerated in frail elderly patients (ECOG ≤ 3) with KRAS wt mCRC and poor prognostic factors in a Phase 2 study of the Spanish Cooperative Group for the Treatment of Digestive Tumours.³² In addition, panitumumab and cetuximab were compared in a randomized Phase 3 study in patients with chemotherapy-refractory KRAS wt mCRC (ECOG ≤ 2).³³ The incidence of adverse events (AEs) of any grade and grade 3-4 AEs was similar across treatment groups.

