8.5 Randomization and Blinding

This is an open-label study. In Part 2, randomization will occur to minimize bias and fulfill a 2:1 ratio between Arm A and Arm B. Prior to randomization, subjects will be stratified according to their KRAS and NRAS mutation status. Randomization will occur via an IRT System until the targeted number of subjects in each treatment-arm is achieved.

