10.3.2 Baseline Assessments (Cycle 1 Day 1, Predose)

At the baseline visit (C1D1), subject eligibility will be confirmed and all questionnaires will be completed prior to the start of any assessments. The following baseline assessments will be performed for all subjects prior to dosing:

- EORTC QLQ-C30
- EORTC QLQ-CR29
- EQ-5D
- Vital signs (body temperature, heart rate, blood pressure, respiratory rate, weight, and height; recorded within 30 minutes prior to start of treatment)
- Physical examination
- ECOG PS
- 12-lead ECG
- Clinical laboratory assessments (hematology, serum chemistry, and coagulation). Immediately prior to Cycle 1, laboratory assessments can be performed either on Day -1 or on Day 1 predose
- Urine dipstick test for women of childbearing potential
- Urinalysis
- For subjects receiving imalumab treatment, blood samples for PK (imalumab plasma levels) and PD biomarkers (oxMIF and total MIF) are to be collected **at any time on Day 1 prior to infusion** (see [Table 6](#)).
- Collection of AEs
- Review of concomitant medications/non-drug therapies
- Entry into IRT System for randomization

See the Schedules of Study Procedures and Assessments ([Table 3](#), [Table 4](#), and [Table 5](#)) for additional details on baseline (Day 1, predose) assessments.

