11.3 Genetic Testing

Genetic testing for KRAS/NRAS mutation status will be performed at screening. If not readily available, genetic testing for KRAS/NRAS mutation status needs to be done early

enough to allow randomization within 4 weeks. If KRAS mutation status is known, the subject can start treatment while NRAS testing is pending.

Dosing regimen for Part 1 is dependent on KRAS/NRAS mutation status. Subjects who are determined to have tumors with KRAS mut, NRAS mut, or both mutations will be assigned to the combination therapy of 5-FU/LV and imalumab. Subjects who are determined to have KRAS wt and NRAS wt tumors will be assigned to the combination therapy of panitumumab and imalumab.

In Part 2 of the trial, subjects will be stratified according to their KRAS/NRAS mutation status and then randomized to Arms A or B in a 2:1 ratio.

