2.2 Inclusion and Exclusion Criteria

2.2.1 Inclusion Criteria

Subjects who meet ALL of the following criteria are eligible for this study:

1. Provision of a signed informed consent
2. Male and female subjects 18 years of age and older at the time of screening
3. Subjects who progressed after receiving at least 2, but no more than 3, prior cancer drug therapy treatment lines including SoC in the metastatic setting
4. Anticipated life expectancy >3 months at the time of screening
5. Weight between 40 kg and 180 kg
6. Histologically or cytologically confirmed diagnosis of CRC
7. Metastatic CRC not amenable to surgical resection
8. Known KRAS, NRAS mutation status (if unknown status for either of these genes and no archival tissue is available, a fresh tumor biopsy will be obtained)
9. At least 1 measurable lesion as defined by RECIST v1.1
10. Eastern Cooperative Oncology Group (ECOG) Performance Status (PS) of 0-2
11. Adequate hematological function, defined as:
 - a. Platelet count $\geq 100,000/\mu\text{L}$
 - b. Prothrombin time and activated partial thromboplastin time (aPTT) < 1.5 times the upper limit of normal (ULN)
 - c. Absolute neutrophil count (ANC) $\geq 1,000/\mu\text{L}$
 - d. Hemoglobin $\geq 9 \text{ g/dL}$, without the need for transfusion in the 2 weeks prior to screening
12. Adequate renal function, defined as serum creatinine ≤ 2.0 times ULN and creatinine clearance $> 50 \text{ mL/min}$ or estimated glomerular filtration rate $> 50 \text{ mL/min}/1.73 \text{ m}^2$
13. Adequate liver function, defined as:
 - a. Aspartate aminotransferase (AST) and alanine aminotransferase (ALT) ≤ 2.5 times ULN for subjects without liver metastases, or ≤ 5 times ULN in the presence of liver metastases
 - b. Bilirubin ≤ 2.0 times ULN, unless subject has known Gilbert's syndrome
14. Adequate venous access
15. For female subjects of childbearing potential, the subject presents with a negative serum pregnancy test at screening and agrees to employ 2 forms of adequate birth control methods, including at least 1 barrier method (eg, diaphragm with spermicidal jelly or foam, or [for male partner] condom) throughout the course of the study and for at least 90 days after the last administration of imalumab. In

addition, these birth control methods must be continued for at least 180 days after last administration of 5-FU in subjects who receive this treatment. Secondary contraceptive measures could be either birth control pills, patches, or intrauterine devices.

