2.4 Randomization

There is no randomization in Part 1. In Part 2, randomization in permuted blocks will occur to minimize bias and fulfill a 2:1 ratio between Arm A and Arm B. Prior to randomization, subjects will be stratified according to their KRAS and NRAS mutation status. Randomization will occur via an IRT System until the targeted number of subjects in each treatment-arm is achieved.

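### Allowing treatment to start with NRAS pending contradicts inclusion criterion 8 and, for a KRAS wild-type subject, leaves the stratum and the Part 1 or Arm A regimen undetermined

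*Protocol*

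**What the plan says.** The allowance is in Protocol 11.3: "If KRAS mutation status is known, the subject can start treatment while NRAS testing is pending". It is repeated in footnote i of Protocol Tables 3, 4 and 5 and of SAP 16.1. The sentence before it in 11.3 asks for testing early enough to permit randomisation within 4 weeks.

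Inclusion criterion 8 (Protocol Synopsis and 9.1) reads "Known KRAS, NRAS mutation status (if unknown status for either of these genes, and no archival tissue is available" and goes on to call for a fresh biopsy in that case. SAP 2.2.1 has the same requirement: "Known KRAS, NRAS mutation status (if unknown status for either of these genes and no archival tissue is available". All inclusion criteria must be met. Protocol 10.3.2 has eligibility confirmed at Cycle 1 Day 1 before dosing and lists "Entry into IRT System for randomization" among the same predose steps.

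On stratification, Protocol 8.5 and SAP 2.4 say "Prior to randomization, subjects will be stratified according to their KRAS and NRAS mutation status". Footnote c of the study schematic (Protocol 20.1) gives two levels, mutated or wild type. SAP 2.4 adds "There is no randomization in Part 1"; there the regimen follows directly from RAS status.

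On regimen, Protocol 6.1.5.4 says "only those with all-RAS wt tumor will be eligible for treatment with panitumumab". Protocol 8.2.2, 8.7.4.2.1 and the Part 1 paragraph of 11.3 give panitumumab to tumours wild type for both genes and 5-FU/LV to tumours with a mutation in either. Protocol 8.2.2 and 8.7.4.2.2 put the same two-gene limit on panitumumab when it is chosen in Arm B.

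**The concern.** The allowance depends on KRAS status being known, whichever way the result falls. Eligibility, stratum and partner drug are all defined on two genes and settled before the first dose. A site cannot follow both sets of instructions, and the allowance stands in five places across the two documents.

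A site that acts on it enters a subject who does not meet criterion 8. If that subject is KRAS wild type, the site must also guess the NRAS result in order to stratify and choose a regimen. A wrong guess puts the subject in the wrong stratum or on a regimen that other passages restrict. No passage covers an NRAS mutation found after treatment has begun: the withdrawal reasons in Protocol 9.3 do not name it, and the general discretion in 9.3 and 10.3.3.1 is not specific to it.

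**Working it through.** No figure in the plan is at issue, so the check applies the plan's own rules to every combination of results. The rules are criterion 8 (both genes known), the stratum rule (mutated if either gene is mutated, wild type if both are wild type), the panitumumab condition (both genes wild type) and the 5-FU/LV condition for Part 1 and Arm A (a mutation found in either gene).

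| KRAS | NRAS | Criterion 8 met | Stratum | Panitumumab condition established | 5-FU/LV condition established |
|---|---|---|---|---|---|
| mutated | mutated | yes | mutated | no | yes |
| mutated | wild type | yes | mutated | no | yes |
| mutated | pending | **no** | mutated | no | yes |
| wild type | mutated | yes | mutated | no | yes |
| wild type | wild type | yes | wild type | yes | no |
| wild type | pending | **no** | **undetermined** | **no** | **no** |

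1. Both pending rows fail criterion 8. Its biopsy clause says how to obtain a missing status; it does not waive the requirement.
2. KRAS mutated, NRAS pending: stratum and partner drug are the same whatever NRAS shows. Criterion 8 is the only conflict.
3. KRAS wild type, NRAS pending: the stratum could still be either one, so the step required before Part 2 randomisation cannot be completed. Neither regimen condition holds, so no regimen can be assigned in Part 1 or Arm A. Exclusion criteria 3, 4 and 6 (Protocol 9.2) also turn on two-gene status, so which of them apply is unknown.
4. Arm B, KRAS wild type, NRAS pending: criterion 8 and stratification conflict in every case. The panitumumab limit is at issue only if panitumumab is the chosen standard of care.

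For the analyses:

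- The primary comparison in SAP 7.1.2 is between the two randomised treatment groups, with an unstratified Cox model, so it does not use the RAS result.
- Protocol 13.4.3.2 reports PFS by KRAS/NRAS stratum, which does use it.
- SAP 5.4 Table 1 labels Arm A cohorts by regimen but Arm B cohorts as SoC Mutated and SoC Wildtype, without saying which RAS result defines them. Summaries that use those two cohorts could be misclassified.
- The response rates by KRAS status in Protocol 13.4.4.3 do not need NRAS.

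**The case against.** The strongest defence is that the allowance governs timing only. It assigns no drug and no stratum, and the next paragraph of 11.3 gives panitumumab only to subjects found wild type for both genes. Read with Protocol 8.5 and 8.2.2, it can operate only for KRAS-mutated subjects, for whom nothing downstream changes. This largely stands as an account of what the rules permit. A reader might infer that the plan authorises panitumumab for a subject with an NRAS mutation; the documents do not support that, because the other rules leave the regimen unassigned rather than granting it. But the allowance is not worded for KRAS-mutated subjects alone: it speaks of known status, and criterion 8 uses the same term for either result. Even on the narrow reading, criterion 8 is still contradicted.

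Other limits also stand:

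- The contradiction concerns only subjects who start under the allowance, not everyone enrolled.
- The Synopsis sentence for Part 1, "Prior to entry into the study, subjects will be stratified according to their KRAS/NRAS mutation status", adds little. Protocol 10.1 counts a subject as enrolled at consent, before screening tests, so its timing is already loose.
- A reader might infer that adverse-event tables for the Arm A cohorts would be wrong. They would not be, because those cohorts are labelled by regimen.
- The randomisation system may block such subjects. Its specification is not in the documents, so this cannot be settled. If it does block them, the allowance grants KRAS wild-type subjects in Part 2 something they cannot use.

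The summary of changes shows that the allowance was added on purpose. That explains its presence but does not align criterion 8 with it.

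**Conclusion.** The inconsistency is real and should be corrected. It is certain on the wording: a subject started with NRAS pending does not meet criterion 8 and, if KRAS wild type, has no determinable stratum and no assignable regimen in Part 1 or Arm A.

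Its practical size is unknown. The documents give no KRAS or NRAS mutation frequency and no indication of how often NRAS would be pending at first dose, so no count can be derived. It is zero if criterion 8 and Protocol 8.5 are enforced as written. The matter bears on eligibility and regimen assignment, and secondarily on PFS by RAS stratum and the two SoC cohorts. It does not touch the sample size or the pooled Arm A versus Arm B comparison.

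**What to change.** The sponsor must reconcile Protocol 11.3, footnote i of Protocol Tables 3 to 5 and footnote i of SAP 16.1 with criterion 8 (Protocol Synopsis and 9.1, SAP 2.2.1), Protocol 6.1.5.4, 8.2.2, 8.5 and 8.7.4.2.2, and SAP 2.4. One consistent rule should cover both KRAS groups and both study parts. If any start with NRAS pending is kept, the text should also say what applies when the later result shows a mutation. Which clinical rule to adopt is the sponsor's decision.

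Optionally, one sentence in SAP 5.4 can state which RAS result defines the RAS strata and the SoC Mutated and SoC Wildtype cohorts. This is a clarification, not the correction of an error. No new listing is needed: KRAS/NRAS status in the disease history (SAP 6.3), the eligibility and randomisation deviation categories (SAP 6.6) and the adverse-event listing with genetic information and actual drug received (SAP 8.3) can identify a discordant subject.

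The cost is wording: at least one protocol section, three protocol footnotes and one SAP footnote, plus the governing passages if the sponsor changes those instead.

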11.4 Tumor-Associated Biomarkers

Tumor-associated genetic alterations in blood and urine (for subjects treated with imalumab in combination with 5-FU/LV or panitumumab who provide consent for optional exploratory biomarker analyses) will be assessed. Genetic changes of cfDNA using whole exome sequencing, targeted NGS strategy or qPCR on a bi-monthly basis will at least cover the genes, such as but not limited to, KRAS, NRAS, APC, p53, BRAF, PIK3CA, since mutations in these genes have been identified as driver mutations in mCRC and/or are responsible for resistance to anti-EGFR therapy. However, in order to identify imalumab-specific patterns of genetic tumor adaption, a larger panel of cancer-related genes will be analyzed.

Blood samples (10 mL) and urine samples (30 mL) for the assessment of genetic biomarkers (cfDNA) will be collected according to the schedule presented in [Table 3](#). Blood and urine samples are to be processed and frozen according to directions provided in the separate laboratory manual. The exact date and clock time of collection of each blood and urine sample should be collected on the eCRF.

The sponsor will obtain available historical tumor mutational testing results for subjects.

12. ASSESSMENT OF SAFETY

12.1 Adverse Events

12.1.1 Definitions

An AE is defined as any untoward medical occurrence in a subject administered an IP that does not necessarily have a causal relationship with the treatment. An AE can therefore be any unfavorable and unintended sign (eg, an abnormal laboratory finding), symptom (eg, rash, pain, discomfort, fever, dizziness, etc.), intercurrent disease (eg,

peritonitis, bacteremia, etc.), or outcome of death temporally associated with the use of an IP, whether or not considered causally related to the IP.

Each Grade 3 or Grade 4 abnormal laboratory value will be reported as an AE, unless the abnormal value relates to a diagnosis that is itself recorded as an AE or has no clinical correlate.

Events relating to clinical deterioration due to disease progression as a result of the underlying malignancy are not to be considered or analyzed as AEs (or SAEs), but will be recorded on the CRF.

A TEAE is defined as any event not present prior to the initiation of the treatments or any event already present that worsens in either intensity or frequency following exposure to the treatments.

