8.2.3 Definition of Dose-Limiting Toxicity

A DLT is defined as any drug-related treatment-emergent adverse event (TEAE) (graded according to the National Cancer Institute Common Terminology Criteria for Adverse Events [NCI CTCAE] v4.03) that occurs during the first 28 days after treatment start and that meets any of the following criteria:

- Any \geq Grade 3 non-hematologic toxicity excluding:
 - a. Mucositis/stomatitis of Grade 3 that resolves to Grade 1 or less with supportive measures within 7 days
 - b. Diarrhea of < 3 days duration following adequate and optimal therapy

- c. Nausea and vomiting of < 3 days duration with adequate and optimal therapy
- d. Fatigue of < 7 days duration following initiation of adequate supportive care
- e. Alopecia
- f. Any single laboratory value out of the normal range that has no clinical significance and that resolves to \leq Grade 2 with adequate measures within 7 days; transient Grade 3 elevations (lasting < 5 days) of hepatic transaminases in the absence of simultaneous increase in serum bilirubin
- Any Grade 4 hematologic toxicity excluding:
 - a. Grade 4 neutropenia lasting for \leq 5 days and not associated with fever
 - b. Isolated Grade 4 lymphocytopenia without clinical correlate
- Grade 3 febrile neutropenia
- Grade 3 thrombocytopenia associated with bleeding
- Any life-threatening complication or abnormality not covered in the NCI CTCAE v4.03

In subjects treated with panitumumab, if a dermatologic reaction develops that is Grade 3 (NCI CTCAE v.4.03) or higher (or is considered intolerable), the dose modifications recommended in the product label will be implemented.³⁴

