8.4 Outcome Measures

8.4.1 Primary Outcome Measure

The primary safety outcome measure is the occurrence of DLTs (Part 1).

The primary efficacy outcome measure is PFS defined as time between treatment initiation and tumor progression (per RECIST v1.1 criteria) or death from any cause, with censoring of subjects who are lost to follow-up or withdraw consent (Part 2).

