12.7.2.1.2 Assessment of Abnormal Laboratory Values

Each Grade 3 or Grade 4 abnormal laboratory value will be reported as an AE, unless the abnormal value is a symptom of, or relates to, a diagnosis that is itself recorded as an AE.

For each other abnormal laboratory value, clinically significant values that are treatment-emergent or that are present at baseline and significantly worsen during the study, in the judgment of the investigator, will be reported as AEs. However, clinically significant

abnormal laboratory values will not be reported as AEs if they meet either or both of the following criteria:

1. Value is associated with the disease being studied, unless judged by the investigator as more severe than expected for the subject's condition.
2. Value is associated with a preexisting condition that has not worsened.

Additional tests and other evaluations required to establish the significance or etiology of an abnormal result or to monitor the course of an AE should be obtained when clinically indicated. Any abnormal value that persists should be followed at the discretion of the investigator.

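### Protocol 12.1.1 and 12.7.2.1.2 give different rules for reporting Grade 3/4 laboratory values as AEs, so a laboratory-only haematologic DLT in Part 1 might go uncounted

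*Protocol*

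**What the plan says.** Two current sections of the protocol state when a Grade 3 or 4 laboratory value must be reported as an AE.

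- Section 12.1.1 requires it "unless the abnormal value relates to a diagnosis that is itself recorded as an AE or has no clinical correlate". That is two exemptions.
- Section 12.7.2.1.2 requires it "unless the abnormal value is a symptom of, or relates to, a diagnosis that is itself recorded as an AE". That is the diagnosis exemption only. The two numbered exemptions that follow are introduced with "For each other abnormal laboratory value, clinically significant values that are treatment-emergent", so they concern values other than Grade 3/4 and do not bring the missing exemption back.

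The term clinical correlate is not defined.

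The DLT definition in 8.2.3 builds on AE status: "A DLT is defined as any drug-related treatment-emergent adverse event (TEAE"), occurring in the first 28 days and meeting a listed criterion. The main haematologic criterion begins "Any Grade 4 hematologic toxicity excluding" and has two exclusions. One is "Isolated Grade 4 lymphocytopenia without clinical correlate". The other is Grade 4 neutropenia lasting at most "5 days and not associated with fever". SAP section 2 repeats this definition.

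Section 8.4.1 ties it to the primary outcome: "The primary safety outcome measure is the occurrence of DLTs (Part 1"). Protocol 13.4.3.1 and SAP 8.1 define the RP2D as the highest dose level with DLTs in fewer than 33% of evaluable subjects.

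**The concern.** The same laboratory value can be a mandatory AE under one section and exempt under the other. Among the haematologic DLT exclusions, lack of a clinical correlate appears only for isolated lymphocytopenia. So 8.2.3 treats other Grade 4 counts as potential DLTs even when the subject has no symptoms, while 12.1.1 allows a site not to report them. Without an AE record there is no TEAE, and without a TEAE the event does not meet the opening words of the DLT definition.

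At stake is the Part 1 DLT count, on which dose escalation and the RP2D rest, in cohorts small enough for a single event to matter. A second consequence is uneven reporting: in both parts, tables of Grade 3 or higher TEAEs depend on which section each site followed.

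**Working it through.** **1. Size of Part 1.** Two combinations, two dose levels and 3 to 6 subjects per cohort give 2 × 2 × 3 = 12 to 2 × 2 × 6 = 24 subjects. This matches the accrual target in the synopsis.

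**2. Which events fall in the gap.** The sections compare as follows.

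| Laboratory-only event | 8.2.3 | 12.7.2.1.2 | 12.1.1 |
|---|---|---|---|
| Grade 4 thrombocytopenia, no bleeding | Meets DLT criterion | Report, unless linked to a recorded diagnosis | May be exempt |
| Afebrile Grade 4 neutropenia, more than 5 days | Meets DLT criterion | Report, unless linked to a recorded diagnosis | May be exempt |
| Isolated Grade 4 lymphocytopenia | Excluded | Report, unless linked to a recorded diagnosis | May be exempt |

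The first two rows are the problem. The SAP 16.2 thresholds for Grade 4 platelets and neutrophils are purely numeric, so both events can arise from a count alone. Febrile neutropenia, and thrombocytopenia with bleeding, carry a clinical correlate by definition and are unaffected.

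**3. Does the SAP resolve it?** No. SAP 8.3 defines a TEAE with no laboratory rule. SAP 8.4 grades laboratory values on their own, apart from AE records.

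**4. Effect of one uncounted event.**

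- First dose level, three subjects: 1/3 = 33.3% becomes 0/3 = 0%. Under 8.2.1.1 the three-subject expansion is skipped and the second level can open after DRC review.
- Six subjects: 2/6 = 33.3%, which is not below 33%, becomes 1/6 = 16.7%, which is.

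**5. Illustration under assumptions.** The documents give neither the true DLT probability p nor the share q of DLTs that are laboratory-only without a clinical correlate, so both are assumed here. The worst case is also assumed: every such event goes unrecorded and is not recovered at DRC review. The apparent DLT rate is then p(1 − q), and P(0/3) = [1 − p(1 − q)]³. For example, p = 0.33 and q = 50% give (1 − 0.165)³ = 0.582.

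| p | q = 0 | q = 10% | q = 25% | q = 50% |
|---|---|---|---|---|
| 0.20 | 0.512 | 0.551 | 0.614 | 0.729 |
| 0.33 | 0.301 | 0.347 | 0.426 | 0.582 |
| 0.40 | 0.216 | 0.262 | 0.343 | 0.512 |
| 0.50 | 0.125 | 0.166 | 0.244 | 0.422 |

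The probability of meeting the <33% rule, by 0/3 or by 1/3 followed by 0/3, is P(0/3) + P(1/3) × P(0/3). At p = 0.33 it is 0.434, 0.500, 0.605 and 0.783 for the four values of q. With q = 0, for instance, 0.301 + 0.444 × 0.301 = 0.434. These figures bound the effect over the assumed range; they do not estimate what happened.

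**The case against.** The strongest reply is that 8.2.3 is the specific rule. If 12.1.1 already removed every Grade 4 value without a clinical correlate, the lymphocytopenia exclusion would be largely redundant. So 8.2.3 presupposes that laboratory-only values can be TEAEs, and an assessor working from it has a clear instruction. Haematology is drawn weekly in Cycle 1. The DRC reviews all safety data (6.5) and determines the RP2D from all data on evaluable subjects (8.2.1). An unexcluded Grade 4 count would probably be seen. SAP 8.4 also tabulates and lists laboratory grades whatever the AE forms say.

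Much of this stands, and it limits the point to a possible loss. It does not remove the conflict. Protocol 15.4.1 says the DRC decides by the DLT-based rules, and no text says that a laboratory value without a TEAE counts as a DLT.

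Four stronger readings are tempting and unsupported.

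- A reader might infer that such values can never be AEs or DLTs. Section 12.1.1 only lifts compulsory reporting, and its own AE definition names an abnormal laboratory finding as an example, so an investigator may still report one.
- A reader might add asymptomatic Grade 4 anaemia. The haemoglobin row for anaemia in SAP 16.2 stops at Grade 3, so the documents supply no laboratory-only Grade 4 anaemia.
- A reader might infer that Grade 3/4 laboratory toxicity is under-reported overall. SAP 8.4 reports it independently; only the TEAE tables are exposed.
- A reader might infer that the RP2D was wrongly set. Nothing in the documents shows that any event was missed.

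**Conclusion.** The inconsistency is real, is in current text, and feeds the primary safety outcome. Its possible size is one decision step per missed event: 1/3 to 0/3, or 33.3% to 16.7% against a threshold of <33%. For a decision to change, a site must have followed 12.1.1 rather than 12.7.2.1.2 and left the value off the AE form, the DRC must not have counted it, and the cohort must have stood where one event matters. The documents give no probability for any of these.

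SAP 5.4 already names 10 mg/kg as the Part 2 dose, so new wording cannot alter the Part 1 escalation. What remains useful is confirming the reported DLT count and making Part 2 TEAE reporting consistent across sites. No view is taken here on which reporting rule is right.

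**What to change.** 1. Reconcile 12.1.1 and 12.7.2.1.2 so that both carry one rule consistent with the DLT definition in 8.2.3, and define clinical correlate if the term stays.
2. For Part 1, compare every laboratory value in the first 28 days that meets the 8.2.3 criteria with the AE and DLT listings. Include non-haematologic Grade 3/4 values outside exclusion (f). An unmatched value needs an assessment of drug relationship before it can be called a DLT. Because scheduled haematology is weekly, a single Grade 4 neutrophil count cannot by itself show whether the episode exceeded 5 days; use any unscheduled results, or flag the case.
3. If any event was missed, correct or footnote the reported DLT count.

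The cost is a short protocol wording change with a clarification to sites, and a listing check on a planned 12 to 24 subjects. SAP 8.3 and 8.4 already call for the AE and laboratory listings, so no new data collection is needed.
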